4.5.8.1 BULBAR AND LIMBAL HYPEREMIA

The redness of the bulbar and limbal conjunctiva of both eyes will be assessed using the EFRON Grading scale (0 to 4, 0 = no redness).

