4.5.8.2 CORNEAL AND CONJUNCTIVAL STAINING

A sodium fluorescein strip, wetted with a few drops of saline, will be applied to the superior bulbar conjunctiva of both eyes. Staining will be graded using the CCLR scale (0 to 100, 0 = no staining) while viewing with cobalt blue light through a Wratten no. 12 barrier filter.

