12 STATISTICAL ANALYSIS AND DATA MANAGEMENT

12.1 STATISTICAL ANALYSIS

[REDACTED]

[REDACTED] Descriptive statistics will be provided on information regarding baseline variables (age, gender, refractive error distribution, etc.).

Approximately 80 participants will be enrolled and randomized. This is an exploratory study and no formal sample size calculation was performed. The results from this study may be used to determine the appropriate time points and power for future studies.

Analysis of variables will be conducted separately on each eye, and data will not be pooled. The study eye will be defined as the qualified eye with the greatest increase in tear production with stimulation by a cotton swab at the Screening Visit (V1). If both eyes qualify and have the same increase in tear production with stimulation by a cotton swab, then the right eye will be designated as the study eye. Table 4 lists the exploratory outcome variables and anticipated statistical procedures.

Table 4: Statistical procedures

Variable	Analysis	Statistical test
Contact Lens Dry Eye Questionnaire-8 (CLDEQ-8), Comfort (scored immediately after insertion, after 2 hours and immediately before lens removal), Comfortable wear time and Total wear time	Descriptive statistics	Mean, Standard Deviation, Min, Max, Count by visit
	Effect of application by visit (comparison of change from baseline between application groups)	t -test / Wilcoxon rank-sum test (as appropriate)
	Stratified analyses by visit (comparison of change from baseline between application groups stratified by CL freq strata and CL type)	t -test / Wilcoxon rank-sum test (as appropriate)
Pre-lens non-invasive tear breakup time (NITBUT) and Tear meniscus height (TMH)	Descriptive statistics	Mean, Standard Deviation, Min, Max, Count by visit
	Effect of application by visit (comparison of change from baseline between application groups)	t -test / Wilcoxon -rank-sum test (as appropriate)

All data will be tested for normality of distribution using Shapiro-Wilk tests. The appropriate test will be selected based on tests of normality.

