The critical alpha level for statistical significance will be set at $p \leq 0.05$, with no adjustments for multiple comparisons. All participants who were evaluated will be used in the analysis. In the event of missing data, individual data points will be excluded in the analysis and not extrapolated from the collected data. As this is a proof of concept, additional statistical analysis may be conducted.

Dependent on the outcome of the study, analysis may be conducted on the contact lenses that have been collected. If the decision is made to not analyse the contact lenses then they will be destroyed according to University guidelines.

Additional analyses may be performed to examine the results observed relative to the device usage recorded by the device itself.

Safety assessments include adverse events, visual acuity and slit lamp biomicroscopy. Summaries by application will be prepared of the number and percentage of subjects reporting one or more adverse events, the number and percentage of subjects reporting one or more device-

related adverse events, the number and percentage of eyes with a clinically significant change in visual acuity at each follow-up exam and the number and percentage of eyes with a clinically significant change in slit lamp biomicroscopy at each visit. A clinically significant change in visual acuity is defined as a change of more than 2 lines (logMAR score change greater than 0.2). A clinically significant change in the slit lamp biomicroscopy parameters will be a change of 2 or more grades.

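### In the readable plan, hyperemia (0-4) and logMAR acuity are summarised by arm only as eyes past a large cut, so a modest average shift would barely show

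*Combined protocol and SAP*

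**What the plan says.** Section 12.1 lists adverse events, acuity and slit-lamp biomicroscopy as the safety assessments, summarised by application. For acuity the summary is "the number and percentage of eyes with a clinically significant change in visual acuity at each follow-up exam". For the slit lamp it is "the number and percentage of eyes with a clinically significant change in slit lamp biomicroscopy at each visit". The slit-lamp cut is defined as follows: "A clinically significant change in the slit lamp biomicroscopy parameters will be a change of 2 or more grades". The acuity cut is more than 2 lines, that is, more than 0.2 logMAR. Neither definition gives a direction, and no test is named for these percentages.

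Table 4 plans means, SDs and between-group comparison of change from baseline for CLDEQ-8, comfort, the two wear times, NITBUT and TMH. It has no row for acuity or for any slit-lamp grade.

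The scales differ. Section 4.5.8.1 has bulbar and limbal hyperemia "assessed using the EFRON Grading scale (0 to 4, 0 = no redness"), with no step size given. Section 4.5.8.2 says "Staining will be graded using the CCLR scale (0 to 100, 0 = no staining"), and section 4.5.8.3 puts palpebral redness and roughness on a 0-100 scale as well.

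Section 12.1 also requires eyes to be analysed separately without pooling, and defines a study eye from the screening Schirmer response. The section opens with redacted blocks, so what follows applies to the readable text.

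**The concern.** Both measures are recorded on graded or near-continuous scales. Reducing each to past or not past a cut discards everything short of it. On a 0-4 scale, a 2-grade change is half the range. An eye that starts above grade 2 cannot worsen by 2 grades, and an eye that starts below grade 2 cannot improve by 2. That follows from the scale alone and needs no assumption about variability.

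At stake is what the safety summary can say about an average effect on the ocular surface or on vision. A sparse pair of counts is compatible with no shift and also with a modest one. It gives the reader no estimate, no interval and no SD, although section 12.1 says the results may inform the power of later studies.

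**Working it through.** The plan states no power, SD or expected rate for these measures, and sections 4.2.1 and 12.1 say the sample size had no formal calculation. There is therefore no stated figure to reproduce.

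**Inputs from the documents.** About 80 participants (section 12.1); cuts of 2 or more grades and more than 0.2 logMAR (section 12.1); hyperemia scale 0 to 4 (section 4.5.8.1).

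**Assumptions.** 40 per arm (the readable text gives no allocation ratio); one value per participant; change normally distributed with mean 0 on sham and a shift on active; a change in either direction counts, because the rule states none. SDs of change are assumed over a range.

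**Step 1: participants past the cut.** With cut c, mean shift m and SD s, P = 1 − Φ((c − m)/s) + Φ((−c − m)/s), and the expected count is 40 × P. For example, with c = 2, m = 0.5 and s = 1.0, P = 0.0668 + 0.0062 = 0.0730, and 40 × 0.0730 = 2.9.

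**Step 2: precision of the mean difference from the same data.** The half-width of the unadjusted 95% CI is t(0.975, 78) × s × √(2/40) = 1.991 × 0.2236 × s = 0.445 × s.

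Hyperemia, shift 0.5 grade:

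| SD | Active past cut, of 40 | Sham past cut, of 40 | CI half-width, grade |
|---|---|---|---|
| 0.4 | 0.004 | 0.00 | 0.18 |
| 0.6 | 0.25 | 0.03 | 0.27 |
| 0.8 | 1.25 | 0.50 | 0.36 |
| 1.0 | 2.9 | 1.8 | 0.45 |

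Acuity, shift 0.05 logMAR:

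| SD | Active past cut, of 40 | Sham past cut, of 40 | CI half-width, logMAR |
|---|---|---|---|
| 0.06 | 0.25 | 0.03 | 0.027 |
| 0.08 | 1.25 | 0.50 | 0.036 |
| 0.10 | 2.9 | 1.8 | 0.045 |
| 0.12 | 5.0 | 3.8 | 0.053 |

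In every row the expected difference between arms is about one participant in 40 or fewer (largest: 4.97 − 3.82 = 1.15).

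**Step 3: how little such counts distinguish (illustrative, since no test is planned).** By Fisher's exact test, 0/40 against 5/40 gives p = 0.055 and 0/40 against 6/40 gives p = 0.026. For the hyperemia shift at SD 0.6, 0.8 and 1.0, power on the counts would be under 0.1%, 0.1% and 1.4%, against 96%, 79% and 60% for a t-test on the means. For acuity at SD 0.12 it would be 2.9% against 45%.

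**Step 4: sensitivity.**
- *Larger shifts.* At SD 1.0, a 1-grade shift puts 6.4 of 40 active participants past the cut, against 1.8 on sham.
- *Both eyes counted.* The expected counts double, for example 5.8 against 3.6 of 80 eyes at hyperemia SD 1.0.
- *Whole-grade recording.* If hyperemia is recorded in whole grades and baselines are spread evenly over 0.5 to 2 (both assumed), rounding puts about 2.1, 4.3 and 6.5 of 40 active participants past the cut at SD 0.6, 0.8 and 1.0, against 0.6, 2.1 and 4.0 on sham. The rows are no longer nearly empty, but the arms still differ by only about 1.5 to 2.5 participants.
- *The 0-100 scales.* Read literally as 2 units, the rule would flag 50% to 89% of eyes with no true shift (SD 3 to 15). Those rows would be crowded, not sparse.

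**The case against.** A count past a clinical threshold is a legitimate safety summary, and this one need not carry the whole safety assessment. Adverse-event tables by application are planned, and section 9.1 records clinically relevant deterioration in a finding as an adverse event. The study is exploratory, section 12.1 leaves room for further analyses, and reduced redness is not among the objectives. A power contrast is also not a criticism of a planned test, because none is planned. How sparse the rows are depends on SDs and a grading step that the documents do not give.

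Most of this stands, and it limits the point. A reader might infer that the safety tables as a whole would be almost empty, or that ocular harm would go unseen. The documents do not support that: adverse events are tabulated separately, the rows are sparse rather than empty at larger SDs or shifts, and the 0-100 rows could fill. Nor can it be said outright that no mean summary is planned, since part of 12.1 is redacted. Whether eyes above grade 2 enter at all is unknown, because the exclusion list in section 4.2.3 is not visible.

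What the objection does not supply is the average change. The adverse-event route depends on a judgement that an individual change is clinically relevant, so it does not estimate a modest mean shift. The clause on further analyses is optional and names no safety variable.

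**Conclusion.** The point holds as a minor improvement. In the readable text, bulbar and limbal hyperemia and logMAR acuity reach the by-arm summaries only as counts of eyes past a cut. For a modest shift (0.5 grade or 0.05 logMAR), those counts would be expected to differ between arms by about one participant in 40 or fewer if grading is fine enough to treat as continuous, and by about 1.5 to 2.5 for hyperemia in whole grades at SD 0.6 to 1.0. The same records would estimate the mean difference to within 0.18 to 0.45 grade or 0.03 to 0.05 logMAR. The size rests on assumed SDs, normal changes and 40 per arm. That the counts discard information below the cut does not depend on those assumptions. The thresholds themselves are not shown to be wrong.

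**What to change.** In section 12.1, keep the threshold counts. Add, for each graded slit-lamp parameter in its own scale units and for logMAR acuity, the mean and SD of change from baseline by application at each follow-up visit. Give the between-arm difference with a 95% CI, adjusted for the baseline value. Use the study eye that 12.1 already defines, which gives one value per participant and respects the rule against pooling eyes. Where grades cluster near zero, add a baseline-to-follow-up shift table by arm, since a mean describes such data poorly. Label all of this as descriptive safety estimation with no claim of significance.

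The cost is a short addition to 12.1 and some extra output from data already collected, with no new visit, procedure or participant. The downside is several more intervals (hyperemia, staining, palpebral redness and roughness, and acuity, at each visit), some of which will exclude zero by chance. The descriptive label is there for that reason.

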12.2 DATA MANAGEMENT

Data from this study will be retained by the CCLR for a minimum of 25 years on a password-protected server. After 25 years, data will be disposed of in accordance with the guidelines laid out by the University of Waterloo.

At the completion of the study the CCLR will provide a copy of the study data to the sponsor when requested. Data will typically be sent using a secure file share system operated by the University of Waterloo called [REDACTED] which uses 128bit (or 256bit) SSL encryption. This system provides a secure way to transfer files when email is not appropriate, whether because of file size, file type or concerns over security. [REDACTED] includes features such as password protection, a restricted time period for download, IP logging and email notification of download. Files may be encrypted prior to transmission at the request of the sponsor. Using this method means that data files are only stored on University of Waterloo servers.

12.3 COMMENTS ON SOURCE DOCUMENTS

Data analysis will not be conducted on comments which have been recorded in the source documents. Only highlighted comments will be entered into the study database. Only relevant and applicable comments will be included in the final report as deemed necessary by the lead investigator.

13 PROTOCOL TRAINING

All study personnel will be required to complete training prior to their involvement in the study. A series of training modules will be developed for the study and records of training will be kept at the CCLR.

14 STUDY MONITORING

Status reports will be provided to the study sponsor by email on a regular basis.

Status reports will include:

- The number of participants screened, enrolled, and randomized (i.e. assigned a study ID number), discontinued and completed.
- Details of protocol deviations.
- Reports of unintended events.

Study monitoring visits may be conducted throughout the study and will be scheduled by the study sponsor in conjunction with the lead investigator. In addition study records may be inspected at the CCLR by the sponsor, the sponsor's designate, the Office of Research Ethics at the University of Waterloo, and by regulatory authorities in Canada and the United States, namely Health Canada and the United States Food and Drug Administration (FDA); however, no records containing identifiable/personal information will be permitted to leave the custody of the CCLR.

15 STUDY MANAGEMENT

15.1 STATEMENT OF COMPLIANCE

This clinical study is designed to be in compliance with the ethical principles in the Declaration of Helsinki, with the ICH guidelines for Good Clinical Practice (GCP), GCP principles described in ISO 14155, the University of Waterloo's Guidelines for Research with Human Participants and with the Tri-Council Policy Statement: Ethical Conduct for Research Involving Humans, 2nd Edition.

- Declaration of Helsinki
- ICH E6 - International Conference on Harmonisation; Good Clinical Practice
- ISO 14155 Clinical investigation of medical devices for human subjects – Good clinical practice
- <http://iris.uwaterloo.ca/ethics/human/guidelines/index.htm>
- <http://iris.uwaterloo.ca/ethics/human/ethicsReview/UWStatement.htm>
- <http://www.pre.ethics.gc.ca/eng/policy-politique/initiatives/tcps2-eptc2/Default/>

15.2 ETHICS REVIEW

This protocol will be submitted to and reviewed through the Office of Research Ethics (ORE) at the University of Waterloo. Notification of ethics clearance of the application is required prior to the commencement of the study.

15.3 PROTOCOL DEVIATIONS

Protocol deviations are unanticipated or unintentional changes to a study after it has received prior sponsor approval and ethics clearance. Protocol deviations can be major or minor.

15.3.1 MAJOR PROTOCOL DEVIATIONS

Major protocol deviations may impact the research protocol, information consent document or other study materials, usually cannot be anticipated ahead of time and are often necessary to ensure the safety and welfare of the participants.

The following are examples of protocol deviations that must be reported to the ORE:

- Changes in procedures initiated to eliminate immediate risks/hazards to participants;
- Enrollment of participants outside the protocol inclusion/exclusion criteria whether agreed to or not by the sponsor;
- Medication / device / intervention errors (i.e. incorrect device / incorrect contact lens(es) dispensed / incorrect care system dispensed);
- Inadvertent deviation in specific research intervention procedures or timing of the research intervention which could impact upon the safety or efficacy of the study-related intervention or upon the experimental design;
- Information consent documentation violations: no documentation of informed consent; incorrect version of, or incomplete, informed consent documentation used.

15.3.2 MINOR PROTOCOL DEVIATIONS

Protocol deviations caused by or which originate with research participants are considered minor, and normally are not reported to the ORE unless they result in increased risk to the participant(s). The following are examples of protocol deviations that are considered minor and do not require reporting to the ORE:

- Logistical or administrative aspects of the study (e.g., study participant missed appointment, change in appointment date);
- Inadvertent deviation in specific research intervention procedures or timing of the research intervention which would not impact upon the safety or efficacy of the study-related intervention or upon the experimental design (i.e., missing a measurement during a session that is not considered critical for the study).

15.3.3 REPORTING AND DOCUMENTING PROTOCOL DEVIATIONS

Major protocol deviations must be reported to the ORE within 7 days of the deviation occurring (or its discovery) using the Protocol Deviation Report Form 107 (PDRF). Information from the PDRF is provided to the Clinical Research Ethics Committee (CREC) at the next monthly meeting.

All protocol deviations (major and minor) occurring during the study will be documented and included in the final report.

15.4 PREMATURE TERMINATION OF THE STUDY

The sponsor, the CCLR or the Office of Research Ethics at the University of Waterloo may terminate the study at any time for any reason.

15.5 STUDY PARTICIPANT RECORDS

Study participant records will be completed to comply with GCP guidelines. Records will contain:

- Unique study acronym and/or code;
- Participant ID;
- Date enrolled;
- Confirmation by lead investigator that participant met eligibility criteria;
- Confirmation that participant received a signed and dated copy of informed consent;
- Exit date;
- Lead investigators signature confirming study exit.

15.6 RETENTION OF STUDY RECORDS AND DATA

Records and data from this study will be retained for a minimum of 25 years. Details regarding storage procedures are given in CCLR SOP 6.3.

16 REPORT

A report will be sent to the sponsor according to terms described in the study contract.

